8.0 Adverse Events and Potential Risks

8.1 Acalabrutinib

See Section 5.3.2 of the Investigator Brochure for further information. A summary is provided here. An aggregate safety analysis of acalabrutinib monotherapy was conducted and included data from 7 studies. This pooled data included 614 acalabrutinib-exposed subjects with a median exposure of 21.9 months. Almost all subjects (609 [99.2%]) had at least 1 AE, and about half (334 [54.4%]) had at least 1 Grade ≥ 3 AE. The most commonly reported AEs of any grade were headache (42.3%), diarrhea (40.4%), fatigue (24.6%), nausea (23.6%), contusion (23.5%), cough (22.1%), and upper respiratory tract infection (21.7). Atrial fibrillation of any grade was seen in

22 (3.6%) patient, grade 3 events were seen in 8 (1.3%) patients, and grade 4 or 5 events were seen in 0 patients. The most frequently reported Grade ≥ 3 AEs were neutropenia (10.4%), anemia (7.5%), pneumonia (6.5%), thrombocytopenia (3.7%), and hypertension (3.1%). Grade 5 AEs were reported for 27 (4.4%) patients with the most common severe AE being infection (2.1%).

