8.3.4 Adverse Event Evaluation

The investigator or designee is responsible for ensuring that all adverse events (both serious and non-serious) observed by the clinical team or reported by the subject which occur on or after cycle 1 day 1 are fully recorded in the subject’s medical records. Source documentation must be available to support all adverse events.

A laboratory test abnormality considered clinically relevant (e.g., causing the subject to withdraw from the study, requiring treatment or causing apparent clinical manifestations, result in a delay or dose modification of study treatment, or judged relevant by the investigator), should be reported as an adverse event.

The investigator or sub-investigator (treating physician if applicable) will provide the following for all adverse events (both serious and non-serious):

- Event term (as per CTCAE v5.0)
- Description of the event
- Date of onset and resolution
- Expectedness of the toxicity
- Grade of toxicity (as per CTCAE)
- Attribution of relatedness to the investigational agent- (this must be assigned by an investigator, sub-investigator, or treating physician)
- Action taken as a result of the event, including but not limited to; no changes, dose interrupted, reduced, discontinued, etc. or action taken with regard to the event, i.e. no action, received conmed or other intervention, etc.
- Outcome of event

Descriptions and **grading scales** found in the NCI Common Terminology Criteria for Adverse Events (CTCAE) version 5 will be utilized for AE reporting. If the event term is not listed in CTCAE v5.0, then the general grading scale shown here will be used.

- Grade 1 (Mild AE) – experiences which are usually transient, requiring no special treatment, and not interfering with the subject's daily activities
- Grade 2 (Moderate AE) – experiences which introduce some level of inconvenience or concern to the subject, and which may interfere with daily activities, but are usually ameliorated by simple therapeutic measures
- Grade 3 (Severe AE) – experiences which are unacceptable or intolerable, significantly interrupt the subject's usual daily activity, and require systemic drug therapy or other treatment
- Grade 4 (Life-threatening or disabling AE) – experiences which cause the subject to be in imminent danger of death
- Grade 5 (Death related to AE) – experiences which result in subject death

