8.5 Reporting Procedures for Serious Adverse Events and AESIs

For the purposes of safety reporting, all adverse events will be reported that occur on or after Cycle 1 Day 1 through the End of Treatment Response Assessment. Adverse events, both serious and non-serious, and deaths that occur during this period will be recorded in the source documents. All SAEs/AESIs should be monitored until they are resolved or are clearly determined to be due to a subject's stable or chronic condition or intercurrent illness(es). Related AEs will be followed until resolution to baseline or grade 1 or stabilization.

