- Concurrent Medications Assessment including prescription medications, over-the-counter (OTC) medications and natural/herbal supplements.
- ECOG Performance Status
- Adverse event evaluation and documentation

- Laboratory Studies:
 - Complete Blood Count (CBC) with differential and platelets
 - Serum Chemistries: Serum chemistry panel: sodium, potassium, chloride, bicarbonate, BUN, creatinine, calcium, glucose, total protein, albumin, alkaline phosphatase, total bilirubin, SGOT [AST], SGPT [ALT]
 - Lactate dehydrogenase (LDH)
- Rituximab administration on days 1, 8, 15, and 22
- Acalabrutinib on days 1-28

Cycles 2-4, Day 1 (for PR responders ONLY)

Cycle 2 should start within 2 weeks after the end of cycle 1 treatment. There is a \pm 3 day window for the start of cycles 3 and 4.

- Physical Examination
- Weight
- Vital signs including: blood pressure, pulse, respiratory rate and temperature
- Concurrent Medications Assessment including prescription medications, over-the-counter (OTC) medications and natural/herbal supplements.
- ECOG Performance Status
- Adverse event evaluation and documentation
- Laboratory Studies:
 - Complete Blood Count (CBC) with differential and platelets
 - Serum Chemistries: Serum chemistry panel: sodium, potassium, chloride, bicarbonate, BUN, creatinine, calcium, glucose, total protein, albumin, alkaline phosphatase, total bilirubin, SGOT [AST], SGPT [ALT]
 - Lactate dehydrogenase (LDH) only on cycle 2 day 1 (not required on cycles 3-4)
- Rituximab administration on day 1
- Acalabrutinib started (continue days 1-28)

End of Treatment Response Assessment – 8 weeks \pm 7 days after treatment completion (this

visit does not apply to subjects with stable/progressive disease after cycle 1)

- Physical Examination
- Weight
- Vital signs including: blood pressure, pulse, respiratory rate and temperature.
- Concurrent Medications Assessment including prescription medications, over-the-counter (OTC) medications and natural/herbal supplements.
- ECOG Performance Status
- Adverse Event Evaluation
- Laboratory Studies:
 - Complete Blood Count (CBC) with differential and platelets.
 - Serum Chemistries: albumin, alkaline phosphatase, total bilirubin, bicarbonate, BUN, calcium, chloride, creatinine, glucose, potassium, total protein, SGOT [AST], SGPT [ALT], sodium
 - Lactate dehydrogenase (LDH)
 - Peripheral blood EBV PCR if positive at baseline

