- PET and diagnostic CT of neck, chest, abdomen, and pelvis with IV and PO contrast for response assessment. Neck CT can be omitted if no involvement at baseline. If insurance only allows one type of scan, PET scan is preferred for end of treatment assessment.
- Disease response assessment

- Bone marrow aspiration and biopsy if positive at baseline
- Peripheral blood sample for correlative studies

Duration of Follow Up

After completion of the study treatment the subjects will be followed for a total of 3 years. The follow up visits will be done at 6, 12, 18, 24 and 36 months after the last cycle of therapy. There is a \pm 14 day window for these visits. If the patient is unable to follow up in person, virtual visits may be used to capture applicable procedures during long-term follow up only.

The follow up visits should include the following:

- Survival/Disease Status
- Physical Examination
- Vital signs
- CBC with differential
- Serum chemistry panel
- Diagnostic CT neck, chest, abdomen and pelvis scan with IV and PO contrast will be done at 6, 12 and 24 months if no disease progression. Neck CT can be omitted if no involvement at baseline
- Peripheral blood EBV PCR if positive at baseline will be done at 6, 12 and 24 months
- Current lymphoma treatment

Patients who have stable/progressive disease are not required to come in for clinical follow up. These patients can be contacted over the phone by the study personnel to obtain the following information

- Survival/Disease Status
- Current lymphoma treatment

Patients will be followed for toxicity until the End of Treatment Response Assessment study visit or until death, whichever occurs first. The clinical course of each event will be followed until resolution, stabilization, or until has been determined that the study treatment or participation is not the cause.

Serious adverse events (SAE) that are still ongoing at the end of the study period will necessitate follow-up to determine the final outcome. Any serious adverse event that occurs after the study period and is considered to be possibly related to the study treatment or study participation will be recorded and reported immediately.

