11.2 Calendar

Procedures	Screening	Cycle 1					Cycles 2-4 ^f	End of Treatment	Long Term Follow Up (± 14 days) ^h				
	Day -28 to Day 1	Day 1 ⁱ	Day 8 (± 2)	Day 15 (± 2)	Day 22 (± 2)	Day 42 (-3)	Day 1	8 weeks ± 7 days after treatment completion	6 Months	12 Months	18 Months	24 Months	36 Months
Medical History	X												
Physical Exam	X	X					X	X	X	X	X	X	X
Vital Signs ^o	X	X	X	X	X		X	X	X	X	X	X	X
Height/Weight	X	X					X	X					
Concurrent Meds Assessment	X	X					X						
Baseline Symptom Assessment	X												
Adverse Event Evaluation		X	X	X	X	X	X	X					
Tumor Tissue	X												
Peripheral Blood Sample	X					X		X					
ECOG Status	X	X					X	X					
CBC w/ differential	X	X	X	X	X		X	X	X	X	X	X	X
PT/INR	X												
Serum Chemistry ^a	X	X		X			X	X	X	X	X	X	X
LDH	X	X					X ^j	X					
Uric acid and phosphorous	X	X											
Pregnancy Test	X ^g												
Urinalysis	X												
Hepatitis Panel	X												
HIV testing	X												
EBV PCR	X ^j				X ^k		X ^k	X ^k	X ^k			X ^k	
ECG	X												
CT Neck/Chest/Abdomen/Pelvis ^c	X ^b				X ^e		X ^e	X ^e	X ^e			X ^e	
PET Scan ^c	X						X						

Bone marrow biopsy/aspiration	X^m							Xⁿ					
Disease Response Assessment						X		X					
Acalabrutinib ^d		X					X						
Rituximab		X	X	X	X		X						
Survival/Disease Status									X	X	X	X	X

- a. Sodium, potassium, chloride, bicarbonate, BUN, creatinine, calcium, glucose, total protein, albumin, alkaline phosphatase, total bilirubin, SGOT [AST], SGPT [ALT]
- b. Neck CT can be omitted at baseline at the discretion of the investigator if there was no suspicion for involvement
- c. PET and diagnostic CT scan preferred, but PET alone is preferred, if unable to obtain both.
- d. Acalabrutinib given on days 1-28
- e. CT neck can be omitted if there was no baseline involvement
- f. For subject in a CR after cycle 1, rituximab will be administered on the same schedule as cycle 1 (see Table 2). For these patients, no other study assessment will be done on days 8, 15, and 22.
- g. Pregnancy test to be done within 72 hours of starting the study drug. This only applies to women of childbearing potential.
- h. Patients with disease progression only need to have survival follow-up and current lymphoma treatment captured (see section 11.1.2). Virtual visits may be used to capture applicable procedures during long-term follow up only if the patient is unable to follow up with the in person.

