14.4 Toxicity Monitoring

Toxicity is defined as any grade 4 adverse event or treatment related death. We will do interim looks for toxicity after every 15 patients have been treated and assessed for toxicity. If the estimated toxicity rate is higher than 20%, we will pause the study and a comprehensive safety assessment will be performed.

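### Section 14.4 scores a fatal adverse event judged unrelated as no toxicity, and patients with stable or progressive disease after cycle 1 have no adverse event evaluation scheduled after the interim visit

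*Combined protocol and SAP*

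**What the plan says.** **The pause rule.** Section 14.4 looks at toxicity after every 15 patients treated and assessed, and pauses for a safety assessment if the estimated rate is above 20%. Its definition is: "Toxicity is defined as any grade 4 adverse event or treatment related death". Section 8.3.4 reserves a separate grade for fatal events; grade 5 covers "experiences which result in subject death".

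**The collection window.** Section 8.5 says that "all adverse events will be reported that occur on or after Cycle 1 Day 1 through the End of Treatment Response Assessment". Section 11.1.2 says of that assessment that the "visit does not apply to subjects with stable/progressive disease after cycle 1". The same section also says: "Patients will be followed for toxicity until the End of Treatment Response Assessment study visit or until death, whichever occurs first". On attendance it adds: "Patients who have stable/progressive disease are not required to come in for clinical follow up". It limits phone contact with these patients to survival or disease status and current lymphoma treatment. The Section 11.2 calendar has no adverse event evaluation in any long-term follow-up column.

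**Two inconsistencies that bear on the window.**
- Footnote h of the calendar says: "Patients with disease progression only need to have survival follow-up and current lymphoma treatment captured". Section 6.5 likewise releases only patients with progression from clinic follow-up, whereas 11.1.2 also releases those with stable disease.
- The interim assessment is at Day 42 with a 3-day earlier window in 11.1.2 and 11.2, at Cycle 1 Day 36 in 6.5, and at days 39-42 after the end of cycle 1 treatment in 3.4.

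**The concern.** The two limbs of the toxicity definition treat attribution differently, and the difference works against the worse outcome. An unrelated sepsis at grade 4 enters the count; the same sepsis, if fatal and with no grade 4 event recorded first, does not. Section 14.4 is the only numeric safety rule in the plan, and its looks are small enough for one patient to decide them.

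The collection gap means that adverse events are observed for different lengths of time according to response. Responders have a scheduled evaluation about 8 weeks after treatment. Patients with stable or progressive disease after cycle 1 have their last one at the interim visit. Any safety summary that pools or contrasts the two groups inherits that difference.

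**Working it through.** Section 14.4 gives no computed figure to reproduce, only the 20% limit and the spacing of looks. The sizes below rest on assumed toxicity rates, because the documents give none for this regimen.

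**1. Trigger counts.** 3/15, 6/30, 9/45 and 12/60 are each exactly 20%, which is not above the limit. A pause therefore needs at least 4/15, 7/30, 10/45 or 13/60. Three counted toxicities plus one unrelated fatal event among the first 15 give 3/15 = 20.0% (no pause) as written, and 4/15 = 26.7% (pause) if the death counts.

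**2. Chance of any pause by 60 patients.** With counted rate p and S(n) the cumulative count, the exact sequential binomial gives

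P(pause) = 1 − P[S(15) ≤ 3, S(30) ≤ 6, S(45) ≤ 9, S(60) ≤ 12].

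Assume a true total rate of 25%, of which u percentage points are patients whose only qualifying event is a fatal event that 14.4 does not count. Then p = 25% − u.

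| u | p | First look | Any pause by 60 |
|---|---|---|---|
| 0 | 25% | 0.539 | 0.864 |
| 1 | 24% | 0.502 | 0.826 |
| 3 | 22% | 0.427 | 0.730 |

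**3. Allowing for futility stops.** The Table 5 boundaries reproduce the early-stopping probabilities in Table 6: 0.173 at a 75% response rate (stated 0.17) and 0.844 at 60% (stated 0.84). Assume toxicity is independent of response and response is known at each futility look. For u = 0, 1 and 3, the chance of any pause is then 0.773, 0.738 and 0.651 at a 75% response rate, and 0.437, 0.413 and 0.358 at 60%.

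**4. Which u is plausible.** The only fatal-event figure is in Section 8.1: "Grade 5 AEs were reported for 27 (4.4%) patients". That is 27/614, from acalabrutinib monotherapy in another population, for all attributions, over a median exposure of 21.9 months. The longest path in this trial, for a partial responder, is 28 + 14 + 84 + 56 = 182 days from first dose to the 8-week visit. At a constant rate, 21.9 months is about 667 days, and 4.4% × 182/667 = 1.2%, before removing treatment-related deaths and patients with a recorded grade 4 event. This is only a guide, but it points to the low end of the table.

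**5. Length of the collection gap.** The last acalabrutinib day of cycle 1 is Day 28.
- Stable or progressive disease, last evaluation at Day 39-42: 39 − 28 = 11 to 42 − 28 = 14 days after treatment.
- Responders: 56 ± 7 = 49 to 63 days after treatment.
- Difference: 49 − 14 = 35 to 63 − 11 = 52 days.

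With the Day 36 date in 6.5 the shorter window is 8 days. With the wording of 3.4 it is 39-42 days, still below 49.

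**6. Effect of the gap on the count.** Assume a 25% true rate, that 25% of patients have stable or progressive disease, and that 10% of their toxicities arise after the interim visit and are all missed. The observed rate is 25% × (1 − 0.25 × 0.10) = 24.4%, and the chance of any pause is 0.841 instead of 0.864. With 40% and 50% in place of 25% and 10%, the observed rate is 20.0% and the chance is 0.612. That extreme needs half of these patients' toxicities to arise late and none to be recorded.

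**The case against.** **Counting only treatment-related deaths is a recognised choice** where background mortality is appreciable. That is fair, but it would argue for an attribution condition on grade 4 events too. The plan has none and does not explain the difference. If grade 4 or higher was meant, the text does not say so.

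**The rule is not the only protection.** A reader might infer that deaths could go unseen. The documents do not support that. Fatal adverse events are serious (8.3.2), go to the sponsor-investigator within 1 business day (8.5.1) and to the Data Safety and Toxicity Committee (8.7), and survival status is followed. The sponsor can suspend the study at any time (6.4). A patient with a grade 4 event recorded before death already counts. What can be lost is a pause, or its timing.

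**The size is easily overstated.** It would be tempting to enter the full 4.4%, or 5 points, as the uncounted share. The source population, its exposure time and its lack of a split by attribution do not support that.

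**The collection gap rarely removes a countable event.** A reader might infer that late grade 4 laboratory cytopenias are routinely lost. Section 8.3.1 makes a laboratory abnormality an adverse event only if clinically significant, and most other grade 4 events would be serious. Possibly related serious events remain reportable after the study period. The loss is mainly non-serious events. Nor is it settled that patients with stable disease stop attending, since 6.5 and footnote h release only those with progression. But even on that reading the calendar gives them no adverse event evaluation, and the follow-up visits start at month 6.

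**Section 11.1.2 offers death as an alternative end of toxicity follow-up.** It does, but no assessment is scheduled to support it for these patients.

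**Conclusion.** Both parts hold on the text, with a limited effect; the change should be made.

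For the definition, an unrelated fatal event with no recorded grade 4 event scores as no toxicity. At an assumed 25% true rate this lowers the chance of any pause from 0.864 to 0.826 for one uncounted point and to 0.730 for three, with one point or less nearer to what the documents suggest. One patient can still decide a look.

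For collection, scheduled evaluation after cycle 1 treatment lasts 11-14 days in patients with stable or progressive disease (11.1.2 dates), against 49-63 days after treatment in responders. This makes non-serious safety data differ by response. Its effect on the pause count is probably small and cannot be fixed from the documents, because 14.4 sets no window for being assessed for toxicity.

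**What to change.** 1. **Section 14.4.** Define toxicity as any grade 4 or grade 5 adverse event, regardless of attribution, with onset from first dose until 8 weeks ± 7 days after the last study dose or the start of non-protocol anti-tumor therapy, whichever is first. Exclude deaths due solely to PTLD progression, in line with 8.3.1. Count any death judged related to study treatment whenever it occurs, and state which of the attribution levels in 8.3.4 are treated as related. Report other grade 4-5 events after non-protocol therapy separately, so that fatal and non-fatal events follow one rule.
2. **Sections 8.5 and 11.1.2.** End adverse event collection for every treated patient at the existing 8 weeks ± 7 days after the last study dose. For patients with stable or progressive disease after cycle 1, do this by adding adverse event questions to a phone contact.
3. **Timing of looks.** If looks are tied to the interim visit so that accrual does not wait, use all toxicity recorded to date and update earlier patients at each later look. Add a final tally once all treated patients have completed collection. Without it, late events in the last cohort, and the two patients after the look at 60, would enter no look.
4. **Reconcile** 6.5 and footnote h with 11.1.2 on who is released from follow-up visits, and 3.4, 6.5 and 11.1.2 on the date of the interim assessment.

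**Cost.** A wording amendment and one phone contact per affected patient. Pauses become somewhat more frequent, including some at true rates within the limit: for example 0.285 at a 15% counted rate against 0.347 at 16%. A pause leads to a review and does not itself close the trial. A judgement remains on which deaths are due solely to progression.

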3.2 Number of Subjects

We plan to enroll 62 patients.

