6.4 Criteria for Removal from Study

Treatment may continue for 2-4 cycles or until one of the following criteria applies:

- Disease progression
- Development of second primary malignancy
- Intercurrent illness that prevents further administration of treatment
- The investigator considers it, for safety reasons, to be in the best interest of the subject
- Unacceptable adverse event(s) (Any toxicity or other issue that causes a delay of study drug administration by more than 4 weeks)
- Subject decision to withdraw from treatment (partial consent) or from the study (full consent),
- Pregnancy during the course of the study for a child-bearing participant
- Death
- Sponsor reserves the right to temporarily suspend or prematurely discontinue this study.

The date and reason for discontinuation must be documented. Every effort should be made to complete the appropriate assessments.

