8.5.1 SAE/AESI Reporting Requirements

- Participating investigators (all sites) must report all serious adverse events and AESIs to the Lead Site Principal Investigator (e.g. Sponsor-Investigator) within **1 business day** of discovery or notification of the event. The participating investigator must also provide follow-up information on the SAE/AESI until final resolution.
 - Please send all SAE/AESI reports to [contact] and cc: [contact] and the study coordinator listed on page 2.
- The Lead Site Principal Investigator will review the SAE and report the event to the FDA, external collaborator(s), and Cleveland Clinic IRB as applicable.
- It is the Sponsor-Investigator's responsibility (e.g. lead site PI) to ensure that ALL serious adverse events that occur on the study (e.g. ALL SAEs that occur at each enrolling institution) are reported to all participating sites.

Drug Supplier / Manufacturer / Financial Supporter Reporting Requirements:

- The investigator is responsible for ensuring that all AEs and SAEs/AESIs that are observed or reported during the study, as outlined in the prior sections, are recorded on the CRF
- It is the responsibility of the Sponsor-Investigator (Cleveland Clinic Principal Investigator) to report safety data to the drug supplier (AstraZeneca Data Entry Site [DES]).
- The Sponsor will submit appropriate reports to applicable local regulatory agencies and to ethics committees (ECs) as per local regulations. The Sponsor will notify Acerta Pharma/AstraZeneca in parallel with submission to the IRB (if applicable) and concerned Regulatory Authority for Suspected Unexpected Serious Adverse Reactions (SUSARs) and within fifteen (15) calendar days of awareness for other SAEs or Special Situation Reports using Form FDA 3500A (MedWatch). New information will be submitted to Acerta Pharma/AstraZeneca within the same time frame as initial reports.
- Whenever possible, SAEs should be reported by diagnosis term not as a constellation of symptoms.
- Death due to disease progression should be recorded on the appropriate form in the electronic data capture (EDC) system. If the primary cause of death is disease progression, the death due to disease progression should not be reported as an SAE to Acerta Pharma/AstraZeneca. If the primary cause of death is something other than disease progression, then the death should be reported as an SAE with the primary cause

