8.7 Data Safety and Toxicity Committee

It is the responsibility of each site PI to ensure that ALL SAEs occurring on this trial (internal or external) are reported to the Case Comprehensive Cancer Center's Data and Safety Toxicity Committee. This submission is simultaneous with their submission to the sponsor and/or other regulatory bodies.

The sponsor-investigator is responsible for submitting an annual report to the DSTC as per CCCC Data and Safety Monitoring Plan.

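### The Section 14.4 toxicity rule waits for each block of 15 to be completed even after the pause at that look has become certain

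*Combined protocol and SAP*

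**What the plan says.** Section 14.4 gives the event, the schedule and the action:

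- Event: "Toxicity is defined as any grade 4 adverse event or treatment related death". A grade 4 event counts whatever its attribution.
- Schedule: "We will do interim looks for toxicity after every 15 patients have been treated and assessed for toxicity". With "We plan to enroll 62 patients" in Section 3.2, the looks fall at 15, 30, 45 and 60.
- Action: "If the estimated toxicity rate is higher than 20%, we will pause the study and a comprehensive safety assessment will be performed".

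The section gives no boundary counts, no look between blocks and no operating characteristics. It does not say whether the rate is cumulative or per block, what counts as being assessed for toxicity, or whether accrual is held while the last patients of a block are assessed.

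Safety oversight elsewhere carries no count. Under Section 8.5.1, participating investigators "must report all serious adverse events and AESIs to the Lead Site Principal Investigator" within one business day. Section 8.7 sends all SAEs to the Data Safety and Toxicity Committee (DSTC) and adds a yearly summary: "The sponsor-investigator is responsible for submitting an annual report to the DSTC". Section 6.4 adds that the "Sponsor reserves the right to temporarily suspend or prematurely discontinue this study". The other formal interim rule, in Section 14.3, concerns response only.

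**The concern.** A count of patients with toxicity cannot fall. Once it reaches the number that will exceed 20% at the next look, the remaining patients in the block cannot reverse the decision to pause. Under 14.4 they may still be enrolled and treated before anyone is required to act. At stake is how many patients start treatment after the protocol's own pause criterion is bound to be met. The gap is widest when the true toxicity rate is high, which is when the rule is most needed.

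The individual reporting routes do not fully cover this. A grade 4 event counts under 14.4, but it need not meet the SAE definition in Section 8.3.2 (a laboratory cytopenia, for example). A tally built from SAE reports alone could therefore miss qualifying events.

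**Working it through.** Section 14.4 states no operating characteristics, so there is no figure of the plan's own to reproduce.

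**Inputs.** Looks at 15, 30, 45 and 60 and a threshold strictly above 20% (14.4); 62 patients (3.2). Assumptions: the rate is the observed proportion of treated patients with toxicity, cumulated over blocks; patients are independent; assessment is immediate; the true rate p lies between 10% and 50%. The documents give no expected toxicity rate for the combination in this population.

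**1. Counts that trigger the pause.** The smallest x with x/n > 0.20:

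- n = 15: 3/15 = 20.0% does not cross; 4/15 = 26.7% does.
- n = 30: 6/30 = 20.0% does not; 7/30 = 23.3% does.
- n = 45: 9/45 = 20.0% does not; 10/45 = 22.2% does.
- n = 60: 12/60 = 20.0% does not; 13/60 = 21.7% does.

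**2. First block.** The fourth toxicity falls at patient m with probability C(m−1, 3) p⁴ (1−p)^(m−4). Summing over m = 4 to 15 gives the probability of a pause at the first look. Averaging 15 − m over the same terms, divided by that sum, gives the mean number of first-block patients treated after the pause is certain.

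| True rate | P(pause at first look) | Mean treated after pause is certain, given a pause |
|---|---|---|
| 20% | 0.35 | 3.5 |
| 30% | 0.70 | 4.6 |
| 40% | 0.91 | 5.8 |
| 50% | 0.98 | 7.2 |

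An extreme case, at least four toxicities in the first five patients, would leave up to 10 more to be treated. Its probability is only 0.007, 0.031, 0.087 and 0.19 at these four rates.

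**3. All four looks.** Let f_i(c) be the probability of c toxicities after i patients with no pause so far: f_i(c) = (1−p) f_{i−1}(c) + p f_{i−1}(c−1). Under the rule as written, probability with c at or above the trigger is removed only at i = 15, 30, 45 and 60. Under the earlier action it is removed at any i, using the trigger for the next look. Mean treated = Σ i × (probability removed at i) + 62 × (probability left).

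| True rate | P(ever pause), both rules | Mean treated, as written | Mean treated, acting at the decisive event |
|---|---|---|---|
| 10% | 0.07 | 59.0 | 58.8 |
| 20% | 0.61 | 39.8 | 37.7 |
| 30% | 0.97 | 22.3 | 18.0 |
| 40% | 1.00 | 16.6 | 10.8 |
| 50% | 1.00 | 15.3 | 8.1 |

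The pause probabilities agree because reaching a trigger count early guarantees crossing at the look, and crossing at the look means the count was reached by then. Only the timing moves.

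**4. Sensitivity to the cumulative reading.** If the rate is taken afresh in each block, the probability of ever pausing is 1 − (1 − P)⁴, with P the chance of at least 4 in 15. At 10%, P = 0.0556 and the result is 0.20. At 20%, P = 0.3518 and the result is 0.82. The cumulative reading gives 0.07 and 0.61, so the choice of reading matters in its own right.

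**The case against.** The best defence is that 14.4 permits continued enrolment but does not require it. Serious events reach the lead site within one business day and also go to the DSTC, and the sponsor can suspend at any time. After four toxicities in five patients, any deaths and other serious events would already be known. Block looks also match the cohort approach of the futility rule, and nothing here is self-contradictory. All of that stands. It makes this an improvement to a safeguard, not an error. What it does not supply is a trigger: discretion carries no count, and non-serious grade 4 events may not travel by the SAE route.

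A second argument is that waiting has some value. The trigger leads to a review, and a review at 15 patients has more data than one at the fourth event, where the observed rate also tends to run high. This is a real trade-off, though the extra data cannot change whether the study pauses.

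Some stronger readings are tempting but not supported:

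- A reader might infer a delay of 18 to 26 weeks by carrying the reporting window in Section 8.5 ("all adverse events will be reported that occur on or after Cycle 1 Day 1 through the End of Treatment Response Assessment") into 14.4. For responders that would be 6 + 4 + 8 = 18 weeks after a complete response, or 6 + 12 + 8 = 26 after a partial response. But 14.4 does not define assessment for toxicity, adverse events are evaluated at every treatment visit including Day 42, and the End of Treatment visit does not apply to patients with stable or progressive disease after cycle 1.
- A reader might infer that no count-based rule exists anywhere. Section 8.8 adopts a centre monitoring plan that is not part of these documents.
- A reader might infer that this is the first use of the combination in this disease. The documents do not say so.

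**Conclusion.** The point holds as a gap in timing. Under 14.4 as written, patients can be enrolled after the pause at the next look is certain. Acting at the decisive event would spare about 4 patients on average at a true rate of 30% (22.3 − 18.0 = 4.3), about 6 at 40% (16.6 − 10.8 = 5.8) and about 7 at 50% (15.3 − 8.1 = 7.2). At 20% the saving is about 2, and at 10% it is 0.2, so the benefit is mainly at high toxicity rates.

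These sizes rest on a cumulative rate, immediate assessment and assumed true rates, and count only to the first pause. Any further delay depends on what assessment for toxicity means and on the speed of accrual. The documents give neither, so I put no figure on it. The first-block arithmetic does not depend on the cumulative reading; the later counts and the unchanged pause probability do.

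**What to change.** In Section 14.4, keep the 20% threshold and the existing action, state that the rate is cumulative over treated patients, and add a sentence such as:

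*If the cumulative number of patients with toxicity reaches the count that makes the next look certain to exceed 20% (4 within the first 15 treated, 7 within 30, 10 within 45, 13 within 60), the study is paused and the comprehensive safety assessment is performed at that point, without waiting for the block to be completed.*

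The lead site should keep a running tally of every event that qualifies under 14.4, including grade 4 events that are not serious. The section should also say what assessment for toxicity means.

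The cost is one paragraph and the tally. On the cumulative reading the probability of pausing is unchanged. The downside is that the safety review sees fewer patients when the pause comes. If the sponsor intended a per-block rate, the count must be set per block instead (4 within any block of 15), because adopting the cumulative counts would then change how often the study pauses.
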